#### 4.5. The CAP Population

The CAP population will include the per-protocol population and who have a final diagnosis consistent with CAP (CAP-radiologically confirmed; CAP not radiologically confirmed, or CAP-no chest radiology done).

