- c. If subject readmitted within 14 days of the qualifying hospitalisation, that follow up hospitalisation will be considered part of the same event as the initial hospitalisation. An additional urine sample will be taken upon readmission.
- d. Any additional results from standard of care pneumococcal and viral respiratory testing, including COVID-19 and RSV, not captured during Visit 1 Day 1 could be recorded at Visit 2 Day 30 (and data can be entered on Visit 1 eCRF).
- e. Any additional information on hospitalisation data electronic case report form (eCRF) items not captured during Visit 1 Day 1 could be recorded at Visit 2 Day 30.
- f. Please see full details of which adverse events to record in Section 16 Table 8.
- g. Information to calculate Charlson Comorbidity Index (CCI) will be collected. Diagnosis codes such as International Classification of Diseases (ICD) discharge codes may be provided as a separate file linked by participant number to calculate CCI or data will be collected via eCRF at Day180 or prior visit.
- h. SOC assessments (for example, details of current illness, vital signs, radiology exams, microbiological testing and others) could be performed before hospital admission or enrolment (Date of Visit) and captured in eCRF.

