study hospitals. Patients with pneumonia who are not enrolled will be recorded on the screening log, which will be the basis of the count of CAP events for incidence estimates. Where appropriate population-based denominators are available, incidence rates for at-risk and high-risk conditions will be generated in aggregate and by condition for more frequent conditions. Nevertheless, incidence estimates will be conservative, given established multiple risks for under ascertainment of pneumonia events in studies in this setting (for example, due to misdiagnosis, chest X-ray [CXR] false negative, or hospitalisation on a different inpatient ward). Non-residents of the hospitals' geographic catchment area will be excluded from incidence estimations.

COVID-19 and pneumococcal infection. The World Health Organization declared COVID-19 a pandemic during the finalization of this protocol (March 11, 2020). On this basis, additional exploratory objectives related to the relationship between COVID-19 and pneumococcal infection were added. If COVID-19 continues to occur at a sufficient frequency in the surveillance region during enrolment to allow for a meaningful analysis, these objectives will be pursued using COVID-19 infection status based on standard –of care testing. Further, if a high incidence of COVID-19 infections is burdening the hospitals at the anticipated time of study start or at some point during study enrolment period, enrolment will be delayed or halted to allow involved staff to focus on COVID-19 clinical care.

This study will prospectively enroll adults, aged 60 years and over, who are hospitalised with CAP in one of the study hospitals: Hospital Universitario de Móstoles, Hospital Universitario Fundación de Alcorcón, and Hospital Rey Juan Carlos de Móstoles (as of February 2022, additional sites may be included at a later date).

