9.1.4. Data Sources

In the Madrid Region, the primary and secondary medical care records are formally linked for routine clinical use. The information related to vaccine administration will be extracted from a population-based computerized vaccination registry that belongs to the Regional Health System, namely SISPAL (http://www.sanidadmadrid.org/saludpublica/e-sispal, restricted access). SISPAL vaccination registry provides nominal records (name, sex, date of birth) of every vaccine administered (vaccine, lot, date of administration) in the public or private sector to the entire population living in the Madrid Region and provides access to the information for every health care practitioner working in the public sector after request. The electronic database was created in 2005 but contains information on vaccination prior to 2005, transferred from manual records. Self-reported vaccination history will not be used as it has been demonstrated that vaccine self-reported data could significantly overestimate the vaccine coverage when compared with SISPAL database.²⁸

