12.1.3. Analysis Populations

12.1.3.1. Vaccine Effectiveness CAP Population (Primary Analysis Population)

The Primary Analysis Population will include all participants who:

- 1. Meet all inclusion and exclusion criteria.
- 2. Have a final diagnosis consistent with CAP (CAP-Radiologically Confirmed; CAP-Not Radiologically Confirmed or CAP-no chest radiology done).
- 3. Meet the definition of either case or test-negative control from Section 12.1.1.
- 4. Have \geq 5 combined years of pneumococcal vaccination history available.
- 5. Did not receive any pneumococcal vaccination ≤30 days prior to urine sample collection.
- 6. Have not received PCV20 if available in surveillance region during study.

This population will be analysed overall and restricted to immunocompetent subjects which will be all subjects not noted to the immunocompromised in Table 7.

Table 7.Categorization of Risk Factors by Immunocompetence³

Risk factor	Spain's Categorization		
Age	60 +		
Diabetes mellitus	immunocompetent		
Alcoholism	immunocompetent		
Chronic heart disease	immunocompetent		
Chronic liver disease	immunocompetent		
Chronic lung disease	immunocompetent		
Smoking	immunocompetent		
Congenital or acquired asplenia	immunocompromised		
Cerebrospinal fluid leak	immunocompetent		
Cochlear implant	immunocompetent		
Congenital or acquired immunodeficiencies	immunocompromised		
HIV infection	immunocompromised		
Chronic renal failure	immunocompromised		
Nephrotic syndrome	immunocompromised		
Leukemia	immunocompromised		
Hodgkin's disease	immunocompromised		
Lymphoma	immunocompromised		
Generalize malignancy	immunocompromised		
Iatrogenic immunosuppression	immunocompromised		
Solid organ transplant	immunocompromised		
Multiple myeloma	immunocompromised		
Antineoplastic chemotherapy	not specified		
Occupational risk with exposure to metal fumes	not specified		
Bone marrow transplantation	immunocompromised		
Neurologic diseases (eg, cerebral palsy and seizures)	not specified		
Prior IPD	immunocompetent		

These populations will serve as the primary analysis population for the primary endpoint and the secondary objective of calculating VE for PPV23.

³ Official Regional Immunisation Programme in the Community of Madrid, 2019.

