#### 2. INTRODUCTION

This statistical analysis plan (SAP) provides the detailed methodology for summary and statistical analyses of the data collected in Study B1851202. This document may modify the plans outlined in the protocol; however, any major modifications of the primary endpoint definition or its analysis will also be reflected in a protocol amendment. Note that any text taken directly from the protocol is *italicized*, with exceptions note where it appears.

This study is designed to evaluate the effectiveness of 13-valent pneumococcal conjugate vaccine (PCV13) in preventing hospitalised vaccine-type (VT) community acquired pneumococcal (CAP) disease among adults aged ≥60 years in Madrid using a prospective study to collect data for test-negative design (TND) analysis, overall and among immunocompetent persons only. Further this study will also measure the proportion of CAP that is associated with Respiratory Syncitial Virus (RSV) infection.

Pneumococcal vaccination status will be based on whether receipt of ≥1 dose of PCV13 or PPV23 could be confirmed by electronic registries. All available vaccination data will be collected from the registry on subjects and time from vaccination will be incorporated in the analysis phase. Patients will be included regardless of the timing of their vaccination relative to their qualifying pneumonia admission but will be excluded from vaccine effectiveness (VE) and serotype distribution analysis if they received pneumococcal vaccination ≤30 days before hospitalisation for CAP because of risk of false positive urinary antigen detection (UAD) test.

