## 6.1.1.1. Primary Endpoint 1- Main Analysis

## Pneumococcal Vaccination Status for Primary Endpoint

Pneumococcal vaccination status is defined as receipt of ≥1 dose of PCV13 or PPV23 and confirmed by electronic registries. Vaccination status will be categorized as: a) never exposed, b) ever exposed. Ever exposed will be subdivided into: i) exposed <5 years, and ii) exposed ≥5 and <10 years. Persons vaccinated ≥10 years will be considered unexposed.

The Madrid vaccination guidelines (Protocol Table 1) stipulate the timing of PCV13, and we will exclude following participants from the VE analyses:

- Immunocompetent participants who received PCV13 within one year after receiving PPV23
- Immunocompromising participants who received PCV13 within eight weeks after receiving PPV23
- Any participants who received PCV20

Note: Cases and controls include either radiologically confirmed CAP, not radiologically confirmed, or chest radiology not done. If more than 5% of the CAP cases are not radiologically confirmed, then a separate analysis will be performed selecting cases and controls only from the radiologically confirmed CAP cases.

The characteristics of cases and controls will be compared using the chi-square test.

DMB02-GSOP-RF02 5.0 Statistical Analysis Plan Template 05-Dec-2019
PFIZER CONFIDENTIAL
Page 31
TMF Doc ID: 98.03

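### The SAP does not carry over the protocol's primary vaccine-effectiveness population: the 5-year vaccination-history criterion is absent and the 30-day vaccination exclusion stands outside the operative sections, with two anchors

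*SAP*

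**What the plan says.** **Protocol.** Section 12.1.3.1 defines the Primary Analysis Population for PCV13 VE and also uses it for PPV23 VE. Criterion 4 requires at least 5 "combined years of pneumococcal vaccination history available". Criterion 5 excludes anyone given a pneumococcal vaccine in the 30 days "prior to urine sample collection". The Summary (Section 3) states the same exclusion but counts back from hospitalisation.

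**SAP.** Section 4 lists the enrolled, per-protocol, CAP, radiologically confirmed and serotype sets and several subpopulations, but no VE set. Section 4.5 says: "The CAP population will include the per-protocol population and who have a final diagnosis consistent with CAP". In 6.1.1.1, under "we will exclude following participants from the VE analyses", there are three items: two rules on the interval from PPV23 to PCV13, and receipt of PCV20. Exposure is never or ever, with ever split by time since vaccination and doses 10 or more years old treated as unexposed. The 30-day exclusion is applied to VE only in the Introduction, as vaccination in the 30 days "before hospitalisation for CAP because of risk of false positive urinary antigen detection (UAD) test". SAP 4.7 repeats it for the serotype set alone, counted from urine collection.

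**Registry and residence.** Protocol 9.1.4 takes vaccination from SISPAL, which records vaccines given "to the entire population living in the Madrid Region", and does not use self-report. The current inclusion criteria (9.1.1) have no residence requirement, and 9.1 removes catchment non-residents from one analysis only: "Non-residents of the hospitals' geographic catchment area will be excluded from incidence estimations".

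**The concern.** The history criterion guards the exposure variable. Status comes from one registry, and a person whom that registry could not have recorded has no dose on file. The protocol removes such a person from VE. The SAP has no unknown category, so the same person becomes never exposed. SAP 5.3 drops participants with missing data from the affected analysis, but nowhere says that absent or short registry history is missing data.

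The 30-day exclusion protects case status, because recent vaccination can turn the urine test positive. A programmer who builds the VE dataset from SAP sections 4 and 6 would not meet it.

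At stake is who is in the primary analysis. Protocol 12.4 and SAP 2 both say that major modifications of the primary endpoint definition or its analysis will be reflected in a protocol amendment. SAP version 3.0 (September 2023) is still tied to protocol version 3.0 (February 2022), so none records this difference.

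**Working it through.** **1. The six criteria side by side**

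| Protocol 12.1.3.1 | Where the SAP has it for VE |
|---|---|
| 1. Inclusion/exclusion met | 4.3, per-protocol |
| 2. Final diagnosis CAP | 4.5 |
| 3. Case or test-negative control | 3.1 and 6.1.1.1 |
| 4. At least 5 years of vaccination history | nowhere |
| 5. No vaccine in the 30 days before urine | Introduction only, counted from hospitalisation |
| 6. No PCV20 | 6.1.1.1 |

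**2. The plan's own sample size.** Inputs from SAP 2.2 and Protocol Table 6: control coverage p0 = 0.15, VE 60% (OR 0.40), alpha 0.025, power 80%, 170 cases and 1,692 controls, Fleiss formula with continuity correction.

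- p1 = OR·p0 / (1 − p0 + OR·p0) = 0.06 / 0.91 = 0.0659
- k = 1692/170 = 9.95; d = 0.15 − 0.0659 = 0.0841; pooled p = (p1 + k·p0)/(1 + k) = 0.1423
- n = [2.241·√(p(1−p)(1+1/k)) + 0.842·√(p1(1−p1) + p0(1−p0)/k)]² / d² = 156.3
- corrected n = (n/4)·[1 + √(1 + 2(1+1/k)/(n·d))]² = 169.2, rounded up to **170 cases**

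The 170 is reproduced with a two-sided 0.025. The 1,692 controls then follow from k, which was taken from the plan, so they are not a separate check.

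**3. Equal registry gaps (assumed).** A share g of cases and of controls has no usable history, is as likely to be truly vaccinated as everyone else, and is coded unvaccinated. Both exposure proportions are multiplied by (1 − g), and VE = 1 − odds(cases)/odds(controls). For g = 5%: cases 0.0626 (odds 0.0668), controls 0.1425 (odds 0.1662), so VE = 1 − 0.0668/0.1662 = 59.8%. Cases needed come from the formula in step 2. The last column is 170/(1 − g), the cases to accrue if these participants are excluded instead.

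| g | Observed control coverage | VE | Cases needed if coded unvaccinated | Cases to accrue if excluded |
|---|---|---|---|---|
| 0 | 15.0% | 60.0% | 170 | 170 |
| 5% | 14.3% | 59.8% | 180 | 179 |
| 10% | 13.5% | 59.6% | 191 | 189 |
| 20% | 12.0% | 59.2% | 218 | 213 |

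The loss of information is nearly the same either way. Exclusion removes the misclassification; it does not buy much power.

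**4. Gaps that differ by case status (assumed)**

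| Gap in cases | Gap in controls | VE | Shift (points) |
|---|---|---|---|
| 5% | 2% | 61.2% | +1.2 |
| 2% | 5% | 58.4% | −1.6 |
| 10% | 5% | 62.0% | +2.0 |
| 5% | 10% | 57.2% | −2.8 |

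**5. The two 30-day anchors.** Let admission be day 0 and urine day u. The hospitalisation anchor excludes doses on days −30 to 0; the urine anchor excludes days u − 30 to u. For u = 2, the first also removes days −30 and −29, which the second keeps, and misses days 1 and 2, which the second removes. So the hospitalisation anchor is the stricter one for every dose before admission. It misses only doses given after admission and up to the urine sample.

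**The case against.** A reader might infer something stronger: that the SAP moved the anchor, that vaccine-induced positive tests therefore enter as vaccinated cases, and that VE is pulled down. The documents do not support this.

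- The SAP did not create the anchor conflict. Its Introduction repeats the hospitalisation anchor of the Protocol Summary, and each document contradicts itself (Protocol Section 3 against 12.1.3.1; SAP Introduction against 4.7).
- By step 5, the hospitalisation anchor already removes the ordinary target, a dose in the month before illness. Visit 1 is normally within 48 hours of admission, and nothing suggests that patients are vaccinated in that window.
- The Schedule of Activities says of early readmissions: "An additional urine sample will be taken upon readmission". No section says that this sample assigns case status.
- A vaccine-induced positive need not be a PCV13 recipient. PPV23 contains 12 of the 13 serotypes in UAD1 (all but 6A), so such a person could be a PCV13-unvaccinated case and push VE up.

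Two further objections limit the history point. Living outside the catchment is not living outside the Madrid Region: the two municipalities hold 6.5% of the Region's older adults, and patients from neighbouring towns should have SISPAL records. The uncovered share may be small. Also, a reasonable team might read the Introduction's 30-day sentence as binding on every VE analysis.

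All of this stands. It does not restore the history criterion, it does not tell the programmer how to code a person without history, and it does not reconcile the anchors.

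**Conclusion.** The point holds as a contradiction between protocol and SAP on the primary population. One of the protocol's six criteria is missing from the SAP altogether; another is left to an introductory sentence, and its anchor needs reconciling in both documents.

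The numerical effect of the missing history criterion on PCV13 VE is probably small: under 1 point for equal gaps up to 20%, and about 1 to 3 points in either direction for the unequal gaps shown. These figures rest on assumed gap rates, because the documents give none. They also rest on the plan's base case (15% coverage, 60% VE), on unadjusted odds ratios, and on uncovered people being vaccinated as often as others.

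No size or direction can be given for vaccine-induced positive tests. Any count of false cases would be invented, and the sign depends on which vaccine was given. The reason to act is that the two documents define different primary populations and the repair is cheap, not that a large bias has been shown.

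**What to change.** 1. Add a VE CAP Population to SAP section 4 with all six criteria of Protocol 12.1.3.1, and run 6.1.1.1, 6.1.1.2 and 6.3.2 on it.
2. Exclude participants with less than 5 years of available vaccination history from VE instead of coding them never exposed. Say what combined years means and how available history is established. Protocol 9.1.4 lists dose-level registry fields, not dates of cover, so this needs a stated source.
3. Put the 30-day exclusion into that population and use one rule in both documents. It should cover doses in the 30 days before admission and doses between admission and the urine sample that sets case status, name that sample, and also work for cases identified by culture alone without a urine result.
4. If the omission was intended, record it in a protocol amendment with the reason.

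The cost is SAP wording, a matching correction to the protocol's 30-day text, and a check of available registry history. The few participants without sufficient history are lost, but the protocol already excludes them, and step 3 of the working shows that keeping them as unvaccinated would save almost no cases.

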## 4.6. Radiologically Confirmed CAP (RAD+CAP) Population

The RAD+CAP population will include the per-protocol population and who have a final diagnosis of radiologically-confirmed CAP.

#### 4.7. Serotype Distribution CAP Population

This population will include the per-protocol population and those who:

have a final diagnosis consistent with CAP (CAP-radiologically confirmed; CAP not

radiologically confirmed or CAP-no chest radiology done).

- did not receive any pneumococcal vaccination ≤30 days prior to urine sample collection,
   and
- pneumococcal serotype identified from UAD1/2 test results, Binax, blood culture or highquality respiratory culture (e.g., from bacterial isolate).

Events with the same serotype result involving rehospitalization  $\leq$ 30 days from the date of discharge of the earlier hospitalization will be considered same event in the analysis.

DMB02-GSOP-RF02 5.0 Statistical Analysis Plan Template 05-Dec-2019
PFIZER CONFIDENTIAL
Page 25
TMF Doc ID: 98.03

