To describe the distribution of S. pneumoniae serotypes using blood, high- quality respiratory cultures, and a serotype- specific urinary antigen detection (UAD) assay among adults 60 years of age and older with CAP.	• Proportion of CAP events for each pneumococcal serotype, PCV-13, and 20-valent pneumococcal conjugate vaccine (PCV20) serotypes among all CAP subjects with UAD1/2 testing (overall) and among all CAP subjects with a pneumococcus identified.	
• To determine the proportion of persons with respiratory pneumococcal carriage among adults 60 years of age and older presenting with CAP by testing saliva specimens using both conventional culture and the sensitive molecular method of PCR for the detection of two target genes (lytA and piaB).	• Proportion of CAP events where the pneumococcus was identified from saliva by culture or PCR divided by all CAP events where the subject had a valid saliva specimen test result.	
• To describe the proportion of participants with CAP and with SP+CAP who present with underlying at-risk and high-risk medical conditions.	• Proportion of CAP subjects with underlying at-risk and high-risk medical conditions, overall and restricted to those with pneumococcus isolated from blood, high-quality respiratory cultures, and a serotype- specific UAD assay.	
• To describe the frequency and type of antibiotic resistance among S. pneumoniae isolates, overall and by specimen type.	• Proportion of S. pneumoniae isolates with antibiotic resistance identified by SOC testing, overall and by resistance type.	

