12.1.3.4. Serotype Distribution CAP Population (Secondary Analysis Population)

The Primary Analysis Population will include all events who:

- 1. Participant meets all inclusion and exclusion criteria.
- 2. Event has final diagnosis consistent with CAP.
- 3. Did not receive any pneumococcal vaccination ≤30 days prior to event urine sample collection.
- 4. Event with valid UAD1/2 test results or other pneumococcal serotype result (eg, from bacterial isolate).

Events with same serotype result involving rehospitalisation ≤ 30 days will be considered same event for this analysis.

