#### 3.2. Secondary Endpoint(s)

 Proportion of CAP events for each pneumococcal serotype, PCV-13, and 20-valent pneumococcal conjugate vaccine (PCV20) serotypes among all CAP subjects with UAD1/2 testing (overall) and among all CAP subjects with a pneumococcus identified.

The denominators for this endpoint are:

- all CAP patients having their UAD 1 or 2 results available,
- all CAP patients with a pneumococcus identified (Sp+) from UAD, Binax, blood culture, or high-quality respiratory cultures

Note: If a participant, for example, is positive for a PCV20 serotype (e.g., 8) and a non-PCV20 serotype (e.g., 17F), the participant will be counted as PCV20 Sp+ and not non-PCV20 Sp+.

 Proportion of CAP events where the pneumococcus was identified from saliva by culture or PCR divided by all CAP events where the subject had a valid saliva specimen test result.

DMB02-GSOP-RF02 5.0 Statistical Analysis Plan Template 05-Dec-2019
PFIZER CONFIDENTIAL
Page 10
TMF Doc ID: 98.03

The denominator will be the CAP population with valid saliva specimen test result.

- Proportion of CAP subjects with underlying at-risk and high-risk medical conditions, overall and restricted to those with pneumococcus isolated from blood, high-quality respiratory cultures, and a serotype-specific urinary antigen detection (UAD) assay.
  - For overall, the denominator will be all CAP population. For participants restricted to pneumococcus, the denominator will be the CAP population in whom a pneumococcus is identified from culture, UAD, or Binax.
- Proportion of S. pneumoniae isolates with antibiotic resistance identified by standard of care testing, overall and by resistance type.

The analysis will be conducted among participants who are Sp+ by culture among the CAP population for whom the data on antibiotic resistance are available. If the antibiotic resistance information is missing or not done for a participant, then the participant will be excluded from the analysis. For participants whose Sp isolates were shipped to the Reference Lab, antibiotic resistance results will be used in the analysis. Participants who are detected as Sp+ via culture method but without serotype information ('Not Serotyped') will also be included in the analysis.

Antibiotic resistance will be reported in the eCRF as one of the following categories:

- SUSCEPTIBLE
- RESISTANT
- NOT APPLICABLE
- o UNKNOWN

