#### 4.8. Sub-Populations

## 4.8.1. Urinary Antigen Detection (UAD) Subpopulation

The UAD subpopulation will include all participants in the per-protocol population that have at least one valid UAD result, i.e., the participants should have UAD results as 'POS' or 'NEG' for any of the 24 serotypes. For each serotype, there are 5 possible values:

- "POS" Positive
- "NEG" Negative
- "INDETERMINATE"
- 4. "QNS" quantity not sufficient
- "NOT DONE" urine was received by VRED laboratory but the test was not done on the sample

The UAD subpopulation will exclude the participants that have

- "INDETERMINATE" results for all 24 serotypes, or
- QNS results for all 24 serotypes, or
- NOT DONE results for all 24 serotypes, or
- had any combination of QNS/ indeterminate/NOT DONE results for all 24 serotypes

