#### 6.2.1.1. Secondary Endpoint 1 - Main Analysis

We will calculate the proportion of participants infected with any of these 20 serotypes (1, 3, 4, 5, 6A, 6B, 7F, 9V, 14, 18C, 19A, 19F, 23F, 8, 10A, 11A, 12F, 15B, 22F, or 33F) as well as for each serotype among all CAP population 60 years or older having their culture and/or UAD test done with the 95% CIs for proportion. Groupings for PCV13 and PCV20 will be included.

The calculations will also be made among the *Sp*+ subpopulation that includes all CAP population in whom a pneumococcus identified by culture, UAD, or Binax.

The subgroup analysis will be done by risk status (high-risk, at-risk, and low-risk), age group (60-74 years,75-84 year and ≥85 years), and by COVID-19 status (COVID-19 positive and COVID-19 negative).

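### SAP 4.7 admits only patients with a serotype identified, contrary to the protocol population of the same name, and the serotype endpoint text does not say whether that set applies

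*SAP*

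**What the plan says.** The protocol's objectives and endpoints table defines the first secondary endpoint with two denominators: the proportion for each serotype and for the PCV13 and PCV20 "serotypes among all CAP subjects with UAD1/2 testing (overall) and among all CAP subjects with a pneumococcus identified". For the matching analysis set, Protocol 12.1.3.4 requires "Event with valid UAD1/2 test results or other pneumococcal serotype result".

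The SAP addresses the denominator in three places:

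- SAP 4.7 carries the same population name but requires a "pneumococcal serotype identified from UAD1/2 test results, Binax, blood culture" or high-quality respiratory culture. It also contains the 30-day vaccination exclusion and a rule merging same-serotype rehospitalisations within 30 days of discharge.
- SAP 3.2 names "all CAP patients having their UAD 1 or 2 results available" and, separately, "all CAP patients with a pneumococcus identified (Sp+) from UAD, Binax, blood culture, or high-quality respiratory cultures".
- SAP 6.2.1.1 computes the proportions in the CAP population "having their culture and/or UAD test done", and again among Sp+ patients.

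Neither 3.2 nor 6.2.1.1 refers to 4.7. SAP Section 2 states in general terms that patients vaccinated within 30 days before hospitalisation are left out of the serotype distribution analysis. SAP 3.4 says that Binax provides no serotype information.

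**The concern.** A valid test is not the same as a serotype found. Under the protocol, a CAP patient with a negative UAD result is in the denominator. Under SAP 4.7 that patient is not. The population that bears the name of the analysis therefore cannot produce its overall figure.

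The SAP 4.7 criterion is also hard to apply as written. Binax cannot supply a serotype. SAP 5.4 counts culture-positive patients who were not serotyped in the serotype distribution, whereas 4.7 read literally removes those with no UAD serotype.

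At stake is the share of hospitalised CAP due to PCV13 and PCV20 types. A programmer who takes the set by its name would report a share of serotyped pneumonia, not a share of tested pneumonia. One who follows 6.2.1.1 keeps the test-negative patients, but starts from a population with neither 30-day rule built in.

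**Working it through.** **1. The plan's own figure.** Protocol 12.1.2 expects about 1,800 CAP admissions a year, 9% of them PCV13-type: 1,800 × 0.09 = 162 a year, and 162 × 4 = 648 over four years. Both match the protocol. The 9% has all CAP as its base.

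**2. The definitions side by side.**

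| Place | Who is in the denominator | Test-negative CAP kept? | 30-day rules built in? |
|---|---|---|---|
| Protocol endpoint, overall | CAP with UAD1/2 testing | Yes | Through 12.1.3.4 |
| Protocol 12.1.3.4 | Valid UAD1/2 or other serotype result | Yes | Both |
| SAP 4.7 | Serotype identified | No | Both |
| SAP 3.2, tested | CAP with a UAD 1 or 2 result | Yes | Neither |
| SAP 6.2.1.1, tested | CAP with culture, UAD or both done | Yes | Neither |

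The last two rows rest on the CAP population of SAP 4.5, which adds only a final diagnosis of CAP to the per-protocol set.

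**3. Size if 4.7 served as the denominator.** Let *s* be the fraction of tested CAP with any serotype identified. The documents do not give it. It cannot be below 9%, because PCV13 types are part of it. I assume 12% to 35%. The PCV13 share becomes 0.09 / *s*:

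| *s* (assumed) | 0.09 / *s* | Inflation 1 / *s* |
|---|---|---|
| 12% | 75% | 8.3 |
| 15% | 60% | 6.7 |
| 20% | 45% | 5.0 |
| 25% | 36% | 4.0 |
| 30% | 30% | 3.3 |
| 35% | 26% | 2.9 |

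**4. Size of the difference between 3.2 and 6.2.1.1.** Protocol Table 6 projects 5% of subjects with no valid serotype result: 1,862 evaluable of 1,960 enrolled (1,862 / 0.95 = 1,960), leaving 98. As an upper bound, suppose that all 98 had a culture only, with a fraction *v* PCV13-type. The share is (0.09 × 1,862 + *v* × 98) / 1,960:

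- *v* = 0: 167.58 / 1,960 = 8.55%
- *v* = 3%: 170.52 / 1,960 = 8.70%
- *v* = 9%: 176.40 / 1,960 = 9.00%

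The largest difference is 9.00 − 8.55 = 0.45 points.

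**5. What is lost if 4.7 is bypassed.** The vaccination exclusion survives through SAP Section 2, but only if the analyst carries it over. Within the SAP, the rehospitalisation rule appears only in 4.7. Protocol exclusion criterion 5 bars re-enrolment up to 14 days after discharge, and Protocol 10.3 gives a re-enrolled patient a new participant number. A readmission on days 15 to 30 with the same serotype could thus count twice. The documents give no frequency for this.

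**The case against.** The strongest reply is that 4.7 does no harm because nothing makes it the denominator. SAP 3.2 repeats the protocol endpoint and names the UAD-tested denominator, 6.2.1.1 also works among tested CAP, and neither mentions 4.7. This stands against a stronger reading that a reader might infer, namely that the reported proportions will not be the among-tested figures. The documents do not support that inference.

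Nor can 4.7 be called binding because it is the only analysis set with the vaccination exclusion. SAP Section 2 states the exclusion independently, so an analyst can apply it without using 4.7. The Sp+ denominator is not a surplus SAP addition either, since the protocol endpoint defines it.

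It can also be argued that 4.7 is a loosely worded base for the Sp+ analysis, with serotype written for pneumococcus. Its list of sources fits that, and it would explain Binax. But this is inference, and the set would still contradict the protocol population of the same name.

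One might go further and demand a valid UAD-1 result for PCV13 and both assays for PCV20, since SAP 4.8.1 asks only that patients "have at least one valid UAD result". Neither the protocol endpoint nor 12.1.3.4 requires this. Protocol 9.1 has both assays run on urine from all enrolled participants, and no figure is given for partial results. The demand would also drop culture-confirmed cases without valid urine whom the protocol population admits.

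**Conclusion.** The contradiction between SAP 4.7 and Protocol 12.1.3.4 is real, and listing Binax as a serotype source conflicts with the SAP's own text. Taken literally, the 4.7 set cannot give the protocol's overall proportion. Beyond that, the finding is an ambiguity: the SAP does not say which set governs the first secondary endpoint, and none of its sets combines test-negative CAP with both 30-day rules.

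The several-fold inflation (9% read as about 26% to 75%) arises only if 4.7 is used as the denominator, and it rests on the assumed 35% to 12% serotype-identified share. The difference between the two tested denominators is minor, at most about 0.45 points if 5% of patients are culture-only and none of them is PCV13-type. The endpoint is secondary and descriptive. The primary VE analysis is not touched.

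**What to change.** - Replace the last criterion of SAP 4.7 with the protocol's: a valid UAD1/2 result, positive or negative, or another pneumococcal serotype result. Delete Binax there.
- Make SAP 3.2 and 6.2.1.1 cite the corrected 4.7 population, so that the vaccination exclusion and the same-event rule apply to the analysis.
- Use one tested denominator in both sections: CAP with UAD1/2 testing, as in the protocol endpoint. This also settles a side effect of the restored criterion, under which patients without UAD enter only when a serotype was found.
- Keep Sp+ as the separate second denominator, with its own definition.

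The cost is SAP wording and the matching programming specification. No new data, samples or protocol amendment are needed.
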